For the monotherapy cohorts of the study, cabiralizumab will be given on Day 1 of each 14-day treatment cycle until the progression of disease, discontinuation of toxicity, withdrawal of consent or study closure. For the combination cohorts of the study, cabiralizumab and nivolumab will be given on Day 1 of each 14-day treatment cycle until the progression of disease, discontinuation of toxicity, withdrawal of consent or study closure. Nivolumab will be administered as an IV infusion over 30 minutes, and then cabiralizumab will be administered as an IV infusion over 30 minutes. This study consists of 2 planned cabiralizumab monotherapy cohorts (M1: 2 mg/kg and M2: 4 mg/kg) and 2 cohorts of cabiralizumab in combination with nivolumab (C1: 4 mg/kg cabiralizumab and 3 mg/kg nivolumab in subjects with solid tumor and C2: 4 mg/kg cabiralizumab and 3 mg/kg nivolumab in subjects with hematologic malignancies). The study design schematic is presented in Figure 1 and Figure 2.

Figure 1: Dose Escalation Schema

[figure not shown]
[figure not shown]

Figure 2. Study Design Schema

A modified Toxicity Probability Interval (mTPI) design will be used to assess the tolerability of cabiralizumab in monotherapy. The DLT evaluation period begins on the first day of treatment and continues for 28 days. Participants who receive at least 2 doses of study drug during the 28-day evaluation interval or participants who discontinue study treatment for drug-related AEs before receiving 2 doses of study drug will be considered evaluable for DLT determination. Dose escalation will be based on the number of DLTs experienced during the DLT evaluation period as determined by the Investigators and Medical Monitor in consultation with Efficacy and Safety Review Committee.

Number of Participants:

This is a Phase 1 study and the sample size cannot be precisely determined and depends on the observed toxicities. Between 6 and 12 subjects are expected to be treated during dose escalation, assuming 2 mg/kg and 4 mg/kg cabiralizumab monotherapy are explored. On the combination cohorts, 6 subjects in each cohort are expected to be treated with 4 mg/kg cabiralizumab in combination with 3 mg/kg nivolumab following the dose escalation part of monotherapy. In addition, Sponsor has the option to expand combination cohorts (up to 12 subjects in total per each

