S: If 6 or more subjects have already enrolled at this dose level, accept the current dose level (4 mg/kg). Otherwise, stay current dose and enroll 3 additional subjects.

D: De-escalate to the lower dose level (2 mg/kg). Accept the lower dose level (2 mg/kg) if 6 or more subjects have already been enrolled at the lower dose level (2 mg/kg).

DU: The current dose is unacceptably toxic. De-escalate to the lower dose level (2 mg/kg) without re-escalation to the current dose level (4 mg/kg). Accept the lower dose level (2 mg/kg) if 6 or more subjects have already been enrolled at the lower dose level (2 mg/kg).

5.1.1.1 *Dose Limiting Toxicity*

Non-Hematologic DLT

A DLT is defined as a study drug-related Non-Hematologic \geq Grade 3 AE (using National Cancer Institute [NCI] Common Terminology Criteria for Adverse Events [CTCAE] v 4.0) occurring during the first 28-days, excluding:

- Grade 3 tumor flare (defined as local pain, irritation, or rash localized at sites of known or suspected tumor),
- Grade 3 rash,
- Grade 3 immune-related adverse event (irAE) that resolved to a Grade 1 or less within 14 days, or a transient (resolving within 6 hours of onset) Grade 3 infusion-related AE.
- Grade 3 or 4 increase in amylase and/or lipase that is not associated with symptoms or clinical manifestations of pancreatitis.
- In the absence of clinical symptoms and other accompanying changes in bilirubin or ALT (as noted in [appendices 6, 7 and 8](#)), serum elevations of AST/ALT $> 12 \times \text{ULN}$ and $\leq 20 \times \text{ULN}$ that last for < 7 days will not be considered a DLT and serum elevations of CK and/or LDH $> 15 \times \text{ULN}$ and $\leq 20 \times \text{ULN}$ that last for < 7 days will not be considered a DLT.

Any recurrence of Grade 3 rash, Grade 3 immune-related AE, or Grade 3 infusion-related AE will be considered a DLT. An irAE is defined as a clinically significant AE that is associated with study drug exposure, of unknown etiology, and is consistent with an immune-mediated mechanism.

Definition of Hematologic DLT

Any of the following study drug-related AEs will be considered a hematologic DLT:

- Febrile neutropenia meeting the following criteria: body temperature $\geq 38.3^{\circ}\text{C}$ at a single measurement, or hyperthermia $\geq 38^{\circ}\text{C}$ with duration ≥ 1 hour AND neutrophil count $< 500/\text{mm}^3$ or $< 1,000/\text{mm}^3$ and predicted to decrease to $< 500/\text{mm}^3$ within 48 hours

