- Grade 4 neutropenia that lasts > 5 days
- Grade 4 thrombocytopenia
- Grade 4 anemia
- Grade 3 thrombocytopenia associated with clinically significant bleeding
- Grade 3 or 4 hemolysis
- Hemotoxicities requiring red blood cell or platelet transfusions.

If the events described above or any other clinically significant events occur, these events will be discussed by the investigator, Sponsor/Medical Monitor and the Efficacy and Safety Review Committee to determine whether they qualify as DLT considering its clinical significance.

Participants who receive at least two doses of study drug during the 28-day evaluation interval or participants who discontinue study treatment due to study drug-related AEs before receiving two doses of study drug will be considered as evaluable for DLT determination.

If doses of cabiralizumab are delayed for more than 28 days during the DLT evaluation period because of study drug related AEs, the Investigator and Sponsor/Medical Monitor will consult the Efficacy and Safety Review Committee and decide whether such events should be classified as a DLT or not, and whether subjects with such events should be considered to be “evaluable” or not.

Unevaluable subjects may be replaced at the same dose level. Subjects who miss a dose during the DLT evaluation period may continue on treatment if the subject does not otherwise meet the criteria for permanent discontinuation in [Section 8](#).

Subjects who withdraw from the study during the DLT evaluation period for reasons other than a DLT are not evaluable for DLT and are replaced at the same dose level. The dose escalation to the next dose level and initiation of combination cohort should be determined in consideration of all safety information, including information on adverse events occurred in subjects excluded from DLT evaluation.

5.1.2 *Cabiralizumab in Combination with nivolumab:*

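### A monotherapy subject who stops before two doses for a drug-related event that is not a DLT is still evaluable, and so counts as DLT-free

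*Protocol*

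**What the plan says.** **DLT definition.** Section 5.1.1.1 counts drug-related non-hematologic events of Grade 3 or worse in the first 28 days, with a list of exclusions. The list includes "or a transient (resolving within 6 hours of onset) Grade 3 infusion-related AE". A recurrent Grade 3 infusion event does count.

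**What happens to treatment.** For a Grade 3 or 4 infusion reaction, Section 7.4.5 says to stop the infusion and give no more drug. Appendix 6 (monotherapy) also says to discontinue at Grade 3 or above. Section 7.4.5 lets clinical judgment modify its recommendations, and Section 8.1.1 allows treatment to restart after consulting the Medical Monitor.

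**Evaluability.** Two doses in the 28-day window make a subject evaluable. So does an early stop: "participants who discontinue study treatment due to study drug-related AEs before receiving two doses of study drug will be considered as evaluable". The Synopsis repeats this: "participants who discontinue study treatment for drug-related AEs before receiving 2 doses of study drug will be considered evaluable for DLT determination".

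**Replacement.** "Subjects who withdraw from the study during the DLT evaluation period for reasons other than a DLT are not evaluable for DLT", and such subjects are replaced. More generally, "Unevaluable subjects may be replaced at the same dose level". Section 8.1 keeps subjects who only stop treatment in follow-up.

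**Who decides.** DLT counts are "as determined by the Investigators and Medical Monitor in consultation with Efficacy and Safety Review Committee" (Synopsis). Section 5.1.1.1 sends the listed events and other clinically significant ones to the same parties "to determine whether they qualify as DLT considering its clinical significance". Escalation must weigh all safety information, "including information on adverse events occurred in subjects excluded from DLT evaluation".

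**The concern.** Early toxicity stoppers are usually kept evaluable because the stop is itself dose-limiting and enters the numerator. Here the evaluability sentence covers any drug-related stop, while the DLT definition excludes some events that end treatment by default. A subject in both categories adds one to the denominator and nothing to the numerator. That subject has had one dose, possibly partial because the infusion was stopped.

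The count guides the escalate, stay or de-escalate action in Table 5.1.1-1. Confirmed tolerability of 4 mg/kg then opens C1 and C2 in parallel (Section 5.1.2). One such stop among three subjects with no DLT reads 0/3, which is E, although only two of the three had the required exposure.

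**Working it through.** **1. One subject through the text.** A subject in M1 has a Grade 3 infusion reaction at dose 1 that clears within 6 hours.
- DLT status: excluded by Section 5.1.1.1 unless the investigator, Medical Monitor and committee decide otherwise.
- Treatment: stopped by default (Section 7.4.5, Appendix 6). If the subject is not redosed, the recurrence rule cannot act.
- Evaluability: yes, because treatment stopped for a drug-related event before two doses.
- Replacement: not triggered. The sentence concerns withdrawal from the study, and this subject stays in follow-up.
- Discretion over evaluability, as distinct from DLT status, is written only for dose delays of more than 28 days.

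The subject enters Table 5.1.1-1 as evaluable with no DLT. A reaction at dose 2 is different, because the two-dose limb is already met.

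**2. Reproducing Appendix 5, Table 3.** I enumerated the Table 5.1.1-1 rules exactly: cohorts of 3, at most 6 per dose, with de-escalation and re-escalation as written. Percentages selecting under 2 / 2 / 4 mg/kg:

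| Scenario (true DLT rates) | Exact | Table 3 |
|---|---|---|
| 1 (0.10, 0.15) | 3.49 / 10.70 / 85.82 | 3.49 / 10.74 / 85.77 |
| 3 (0.15, 0.25) | 8.10 / 25.18 / 66.72 | 8.19 / 25.13 / 66.69 |
| 5 (0.25, 0.33) | 22.46 / 37.29 / 40.25 | 22.46 / 37.17 / 40.36 |

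Scenarios 2 and 4 also agree within 0.2 points.

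**3. Effect of replacing these subjects.** Let r be the probability that a subject without a DLT stops early for a non-DLT drug-related event. The documents give no value, so r = 1%, 5% and 10% are assumed, equal at both doses and independent of DLT. Table 3 is taken as performance under the current wording, where a stopper counts as no DLT and the observed rate is p. If stoppers are replaced, the rate among evaluable subjects is

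p' = p / (1 − (1 − p)r).

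Scenario 3, r = 10%: 0.15/(1 − 0.085) = 0.1639 and 0.25/(1 − 0.075) = 0.2703. Scenario 5, r = 10%: 0.25/(1 − 0.075) = 0.2703 and 0.33/(1 − 0.067) = 0.3537. Putting p' through the same enumeration gives P(accept 4 mg/kg):

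| Scenario | Current | r = 1% | r = 5% | r = 10% |
|---|---|---|---|---|
| 1 | 85.8% | 85.6% | 84.5% | 83.0% |
| 3 | 66.7% | 66.3% | 64.3% | 61.7% |
| 5 | 40.3% | 39.7% | 37.5% | 34.7% |

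Expected replacements are the sum over doses of E[evaluable n] × (1 − p)r / (1 − (1 − p)r). At r = 10%:
- Scenario 1: 3.99 × 0.090/0.910 + 3.72 × 0.085/0.915 = 0.74.
- Scenario 5: 4.78 × 0.075/0.925 + 2.64 × 0.067/0.933 = 0.58.

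**4. The other baseline.** Table 3 can instead be read as describing fully exposed subjects, diluted by stoppers. If a stopper carries a share f of the 28-day DLT risk, the apparent rate is (1 − r)p + r[1 − (1 − p)^f]. In Scenario 5 at r = 10%, selection of 4 mg/kg under the current wording rises from 40.3% to 43.8% (f = 0.5) or 48.0% (f = 0). The direction is the same.

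**5. One cohort of three.** At a true rate of 0.33, three fully exposed subjects give E with probability 0.67³ = 0.301. If one is an uninformative stopper counted as DLT-free, this becomes 0.67² = 0.449.

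**The case against.** The strongest reply is that the case is narrow and people decide it. Section 7.4.5 describes Grade 3 reactions partly by symptoms needing 6 hours or more to respond, which largely fall outside the exclusion, and a recurrent Grade 3 reaction is a DLT. The subject may be redosed. Any Grade 3 reaction is reported to the Medical Monitor within 24 hours, and one that ends treatment could well be judged a DLT. Table 5.1.1-1 is headed as guidance, and the committee must agree to escalation on the totality of safety data. All of this stands and keeps the point minor. None of it takes the subject out of the denominator once the event is judged not a DLT.

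It could also be said that the replacement sentence already covers the subject. It speaks of leaving the study. If read to include stopping treatment, it would contradict the evaluability sentence for the same person, so the wording needs repair on either reading.

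The numbers are open to fair criticism too. The stop rate has no source, and the documents do not settle which baseline in the working applies. In Scenarios 1 and 3 the rate at 4 mg/kg stays at or below 30% even after adjustment (0.1639 and 0.2703 at r = 10%), so there the change means selecting an acceptable dose less often. Only in Scenario 5, where 4 mg/kg exceeds the 20–30% interval, is the fall clearly protective.

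Finally, whether to keep, replace or count such stoppers is partly a design choice. That is true, but the current rule is the least cautious of the three.

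**Conclusion.** The point holds as a minor gap in the evaluability rule. A drug-related stop before two doses that is not called a DLT adds a DLT-free subject without the two-dose exposure asked of other DLT-free subjects, which tilts the count slightly towards escalation. At r = 1% the shift in P(accept 4 mg/kg) is about 0.2 to 0.5 points, and at r = 10% about 3 to 6 points. These figures assume that r, with no stopper redosed or judged a DLT, and take Table 3 as performance under the current wording. They illustrate the size and do not measure it.

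A reader might infer more, and the documents do not support it:
- *That escalation would follow automatically or the event would be lost.* The committee reviews all safety data, and AEs leading to discontinuation are part of the primary endpoint.
- *That the infusion-reaction exclusion is wrong.* It is a reasonable definition, and the parties may still call the event a DLT.
- *That Appendix 5 is in error.* Its mTPI selection percentages reproduce.

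**What to change.** Leave the DLT exclusions as they are. In Section 5.1.1.1 and the Synopsis, replace the evaluability sentence with wording such as:

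> A participant is evaluable for DLT after two or more doses within the 28-day window, or on having a DLT at any time in that window. A participant who permanently stops treatment for a drug-related AE before having received two doses, where the event is determined not to be a DLT, is not evaluable and is replaced at that dose level. The Efficacy and Safety Review Committee reviews the event before escalation.

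This keeps the existing two-dose standard and treats every excluded event that ends treatment alike, so the infusion item needs no separate patch. Counting such stops as DLTs remains a sponsor option.

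The cost is an occasional replacement subject, fewer than one expected over the whole escalation at r up to 10%, each adding a further 28-day evaluation period for that cohort. No new data are needed: the CRF already records the amount infused after a Grade 3 or 4 reaction and the reason for discontinuation. Section 5.1.1.1 already provides for replacement and for reviewing events in excluded subjects.

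### The trigger for committee review of DLT evaluability cannot be met inside the 28-day window, so a one-dose subject with a laboratory DLT can miss both stated routes and be replaced

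*Protocol*

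**What the plan says.** The Synopsis fixes the window: "The DLT evaluation period begins on the first day of treatment and continues for 28 days". Dosing is every 14 days (Protocol Section 5.1), so dose 2 is due on Day 15.

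Section 5.1.1.1 gives two routes to evaluability. The first, by dosing, covers "Participants who receive at least two doses of study drug during the 28-day evaluation interval". The second, by stopping early, covers "participants who discontinue study treatment due to study drug-related AEs before receiving two doses of study drug". For other cases the investigator and sponsor consult the Efficacy and Safety Review Committee on both DLT status and evaluability, but only on this condition: "If doses of cabiralizumab are delayed for more than 28 days during the DLT evaluation period because of study drug related AEs". Then "Unevaluable subjects may be replaced at the same dose level", while "Subjects who miss a dose during the DLT evaluation period may continue on treatment" provided no permanent-discontinuation criterion in Section 8 is met.

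Two other sentences in the section bear on this. One sends events to the committee "to determine whether they qualify as DLT considering its clinical significance"; it concerns the event, not whether the subject is counted. The other requires decisions on escalation and on opening the combination cohorts to take in all safety information, "including information on adverse events occurred in subjects excluded from DLT evaluation".

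Neither Protocol Section 10.2 nor SAP Section 6.3 defines a DLT-evaluable population, so the rule in Section 5.1.1.1, whose two routes the Synopsis repeats, is the only one.

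**The concern.** The evaluability clause is set at a delay longer than the window it refers to. Nothing else in the section says that a subject with a DLT counts. A subject can therefore have a DLT during the window, stay on treatment on hold, and end the window with one dose and no discontinuation. As written, that subject is unevaluable and may be replaced, which takes a real DLT out of the count that the modified toxicity probability interval (mTPI) table uses.

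With cohorts of 3 or 6, one subject can change the decision: Table 5.1.1-1 reads Stay at 1/3 and Escalate at 0/3. Confirmed tolerability at 4 mg/kg also opens both combination cohorts (Section 5.1.2), with up to 24 patients.

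**Working it through.** **1. The plan's own figure.** Exact enumeration of the decision table (cohorts of 3, at most 6 per dose) gives 85.82, 81.05, 66.72, 57.84 and 40.25% of trials selecting 4 mg/kg in Appendix 5 scenarios 1 to 5. Appendix 5 Table 3 states 85.77, 81.16, 66.69, 57.85 and 40.36%. All agree within 0.2 points, so the decision rules used below are those of the plan.

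**2. Days.** Inputs: dose 1 on Day 1, dose 2 due on Day 15, window closing on Day 28.
- On Day 28 dose 2 is at most 28 − 15 = 13 days late, and 28 − 1 = 27 days have passed since dose 1.
- More than 28 days is first reached on Day 1 + 29 = Day 30, or on Day 15 + 29 = Day 44.
- Delays of 14 to 28 days from Day 15 put dose 2 on Days 29 to 43, which is 15 possible days.

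| Reading of the clause | First acts | Reaches dose 2 on |
|---|---|---|
| Delay must lie inside the window | never | no day |
| Counted from Day 15, may run past the window | Day 44 | none of Days 29–43 |
| Counted from dose 1, may run past the window | Day 30 | Days 30–43 (14 of 15), not Day 29 |

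Section 8.1.1 counts its six-week limit from the previous dose. Section 5.1.1.1 gives no starting point.

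**3. Can a subject get there by following the protocol?** Take ALT 15 x ULN with no symptoms or bilirubin change, found at the scheduled Day 8 test and above 12 x ULN until Day 30.
- *DLT status.* Section 5.1.1.1 excludes AST/ALT >12 to 20 x ULN and CK/LDH >15 to 20 x ULN only when they last under 7 days. This one reaches 7 days on Day 15. At 22 days it is also beyond the 14-day exclusion for immune-related events.
- *Treatment.* Appendix 6 delays dosing, resumes it at 12 x ULN or below, and stops it only if the elevation lasts more than 28 days or worsens. For onset on Day 8 that limit passes on Day 37; for onset on Day 15, on Day 44. Appendix 8 sets the same limit for CK/LDH.
- *No forced stop.* Section 8.1.1 exempts Grade 3 laboratory abnormalities (thrombocytopenia apart) and Grade 4 CK up to 20 x ULN without clinical sequelae.
- *Result.* On Day 28 the subject has one dose, a DLT and no discontinuation. Neither route is met.

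Most other Grade 3 drug-related events lasting more than 7 days require discontinuation under Section 8.1.1, so those subjects stay evaluable. The same is true if the enzyme elevation persists past the Appendix limit and treatment stops.

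**4. Effect on the decision at 2 mg/kg.** Condition: a first cohort of 3 with one DLT, in the held subject; the table is followed without committee override. *p* is the true DLT rate, at the two ends of the Appendix 5 range for this dose.
- Subject counted: 1/3 is Stay, and escalation needs no DLT in three more: (1 − p)³.
- Subject dropped and replaced: (1 − p) + p(1 − p)³.
- Subject kept and a fourth added: Appendix 5 Table 1 reads 1/4 as Escalate and 2/4 as De-escalate, which stops enrollment at the starting dose, so the chance is 1 − p.

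| p | Counted | Dropped and replaced | Kept, fourth added |
|---|---|---|---|
| 10% | 0.9³ = 0.73 | 0.9 + 0.1 × 0.729 = 0.97 | 0.90 |
| 25% | 0.75³ = 0.42 | 0.75 + 0.25 × 0.422 = 0.86 | 0.75 |

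**5. The opposite direction.** Grade 2 periorbital edema held beyond 14 days (Appendix 6) is a non-DLT hold. Replacing that subject in a 0/3 cohort lowers the chance of escalating from 1.00 to 0.97 or 0.86, because the replacement may have a DLT. The rule is unstable in both directions.

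**The case against.** The case against has real substance.

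- *Intent.* Section 5.1.1.1 treats withdrawal as non-evaluable only when the reason is something other than a DLT, and the Synopsis bases escalation on DLTs determined in consultation with the committee. The drafters plainly did not mean to discard DLTs. This stands as evidence of intent, but no sentence says it for a subject held on treatment.
- *Counting from dose 1.* On the Section 8.1.1 convention, and if the clause may act after Day 28, the committee could decide for re-dosing on Days 30 to 43. This stands. A reader might infer that the subject can never be evaluable; that follows only if the clause is read literally or the delay is counted from Day 15.
- *Timing.* A reader might infer that the clause cannot act before the table is read. In a first cohort of 3 the documents do not support this. Dropping one subject leaves 2, for which neither table has a column. A replacement started on Day 29 completes 28 days on Day 56, after both Day 30 and Day 44.
- *Denominator.* Both tables are indexed by subjects treated, so a reader may keep the DLT and read 1/4. This is a fair reading. It still gives Escalate where 1/3 gives Stay, so the evaluability call still drives the decision.
- *Safeguards.* Escalation needs committee agreement on all safety data, and replacement is optional. The committee can override the table, but neither safeguard puts the DLT back into the count.

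**Conclusion.** The point holds as a defect of wording with a narrow but real consequence. The only evaluability referral uses a threshold that cannot be reached inside the window, and a DLT does not by itself make a subject evaluable. Someone following the text can drop a true DLT from the dose-decision count and move from Stay to Escalate.

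The size is conditional: 0.73 to 0.97, or 0.42 to 0.86, for escalation at 2 mg/kg if the DLT is dropped; 0.90 or 0.75 if it is kept and a fourth subject is added. These figures assume one such event in a first cohort of 3, a replacement or added subject, and no committee override. How often this would happen cannot be derived from the documents, so no trial-level effect is claimed.

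A reader might also infer that the primary safety endpoint loses the event. It does not follow: Protocol Section 10.3.2 runs all safety analyses on the Treated population, so the adverse event stays in those tables. What is affected is the dose-decision count.

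**What to change.** Change Section 5.1.1.1 in two places, and carry the first into the Synopsis.

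1. Add: *Any subject who has a DLT in the 28-day period is evaluable, whatever the number of doses received.*
2. Replace the trigger of more than 28 days with: *If the second dose is not given by Day 28 because of a study drug-related AE, the Efficacy and Safety Review Committee decides DLT status and, where no DLT is assigned, evaluability, before the subject is replaced and before the decision table is read.*

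The first sentence keeps every DLT in the count. The second covers the non-DLT hold and removes the doubt about where a delay starts. The cost is an occasional extra consultation before a held subject is replaced, and slightly fewer escalations when a one-dose DLT is counted.

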5 STUDY DESIGN

5.1 Overall Design

This study is a Phase 1, open-label, dose escalation study to evaluate the safety, tolerability, PK, and PD and preliminary anti-tumor activity of cabiralizumab as monotherapy in subjects with advanced solid tumor. In addition, the study will evaluate the safety profile, PK, PD and preliminary anti-tumor activity of cabiralizumab in combination with nivolumab in subjects with advanced solid tumors and hematologic malignancies.

For the monotherapy cohorts of the study, cabiralizumab will be given on Day 1 of each 14-day treatment cycle until the progression of disease, discontinuation of toxicity, withdrawal of consent or study closure. For the combination cohorts of the study, cabiralizumab and nivolumab will be given on Day 1 of each 14-day treatment cycle until the progression of disease, discontinuation of toxicity, withdrawal of consent or study closure. Nivolumab will be administered as an IV infusion over 30 minutes, and then cabiralizumab will be administered as an IV infusion over 30 minutes.

This study consists of 2 planned cabiralizumab monotherapy cohorts (M1: 2 mg/kg and M2: 4 mg/kg) and 2 cohorts of cabiralizumab in combination with nivolumab (C1: 4 mg/kg

cabiralizumab and 3 mg/kg nivolumab in subjects with solid tumor and C2: 4 mg/kg cabiralizumab and 3 mg/kg nivolumab in subjects with hematologic malignancies).

The study will consist of 3 periods: Screening, Treatment and Follow-up. The study will end after the last subject completes the last visit.

Screening begins by establishing the subject's initial eligibility and signing of the informed consent form (ICF). Subjects must have treatment assignment within 28 days after signing the informed consent.

The Treatment Phase begins when the treatment cohort is assigned to the subjects. The subject will be assigned to the open cohort (M1, M2, C1, or C2) at the timing of the treatment assignment. First dose should be started within 3 days of treatment assignment. The subjects will be required to be hospitalized for safety evaluation at least for 8 days from the first dose. The subjects can be discharged at the investigator's discretion at Day 8.

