7.5.1 Dosing of Cabiralizumab and Nivolumab

For patients in the monotherapy cohorts, cabiralizumab infusion will be administered as a 30-minute IV infusion on Day 1 of each 14-day treatment cycle. For the combination therapy, nivolumab should always be administered first as a 30-minute IV infusion followed by a 30-minute infusion of cabiralizumab. The time in between infusions is expected to be approximately 30 minutes but may be more or less depending on the situation. Cabiralizumab ± Nivolumab will be administered every 2 weeks in 14-day (\pm 2 days). Subjects may be dosed no less than 12 days from the previous dose.

Dosing calculations should be based on the body weight assessed at Cycle 1 Day 1 prior to the first dose of study drug administration. If the subject's weight on the day of dosing differs by $> 10\%$ from the weight used to calculate the prior dose, the dose must be recalculated. All doses should be rounded to the nearest milligram.

The calculated dose for Cabiralizumab may be mixed in 5% Dextrose Injection, USP or 0.9% Sodium Chloride Injection, USP to nominal concentrations of 1.0 mg/mL to 10 mg/mL which can be infused over a period of 30 minutes through an intravenous line containing a sterile 0.22 micron in-line filter. Further guidance and information for the preparation of the study medication is provided in the pharmacy manual.

The calculated dose for Nivolumab may be mixed in 5% Dextrose Injection, USP or 0.9% Sodium Chloride Injection, USP to nominal concentrations of 1 mg/mL – 10 mg/mL which can be infused over a period of 30 minutes through an intravenous line containing a sterile, non-pyrogenic, low-protein binding in-line filter. Further guidance and information for the preparation of the study medication is provided in the pharmacy manual.

[figure not shown]
Doses of study drugs may be interrupted, delayed, or discontinued depending on how the patient tolerates the treatment.

[figure not shown]
[figure not shown]
[figure not shown]
7.5.2 *Retained Samples for Bioavailability / Bioequivalence*

Not Applicable.

7.6 *Treatment Compliance*

Study treatment compliance will be periodically monitored by drug accountability. Drug accountability should be reviewed by the site study staff at each visit to confirm treatment compliance. Sites should discuss discrepancies with the participant at each on-treatment study visit.

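### Section 5.1.1.1 makes a participant who takes two doses, then withdraws from the study before Day 28 without a DLT and for a non-DLT reason, both DLT-evaluable and not evaluable, with no stated precedence

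*Protocol*

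**What the plan says.** Protocol Section 5.1.1.1 first defines evaluability by exposure: "Participants who receive at least two doses of study drug during the 28-day evaluation interval" count as evaluable, as do participants who stop treatment for drug-related AEs before a second dose. It does not require observation to the end of the window. Two paragraphs later it defines evaluability by withdrawal: "Subjects who withdraw from the study during the DLT evaluation period for reasons other than a DLT are not evaluable for DLT", and these subjects are replaced at the same dose level. This sentence makes no exception for people who have had two doses.

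The synopsis repeats the exposure rule ("Participants who receive at least 2 doses of study drug during the 28-day evaluation interval") and omits the withdrawal rule. The SAP does not settle the matter: its Section 6.3 defines Enrolled, Treated, Pharmacokinetic and Immunogenicity populations, but no DLT-evaluable set.

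On timing, "The DLT evaluation period begins on the first day of treatment and continues for 28 days", while "cabiralizumab will be given on Day 1 of each 14-day treatment cycle", and Section 7.5.1 adds: "Subjects may be dosed no less than 12 days from the previous dose". In Table 5.1.1-1, 0/3 reads E, 1/3 reads S and 1/6 reads E.

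**The concern.** The second dose falls near the middle of the window, so anyone who takes it and then leaves the study before Day 28 for a non-DLT reason meets both rules. The classification decides whether that person adds a DLT-free unit to the denominator or is replaced.

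The DLT count drives the escalation decision. At 4 mg/kg, a reading of E accepts the dose, possibly on three participants. Confirmed tolerability there, with committee agreement, opens both combination cohorts in parallel (Section 5.1.2). In a cohort of three, one partly observed person is a third of the evidence, and any error from counting that person favours escalation.

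The unobserved half matters. Several DLT criteria depend on duration, such as Grade 4 neutropenia beyond 5 days or enzyme elevations judged against a 7-day limit. Under Table 2-2, the first routine laboratory visit after an on-schedule second dose is Cycle 3 Day 1, about Day 29, unless an end-of-treatment visit takes place.

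**Working it through.** **1. Do the rules overlap?** Dose 2 is due on Day 15, or Day 13 at the earliest (12 days after dose 1). Someone who leaves just after dose 2 has been observed for f = 12/28 = 43% to 14/28 = 50% of the window. Take doses on Days 1 and 15, withdrawal of consent on Day 18, no DLT, and two other cohort members who are DLT-free:

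| Rule applied | Status of the leaver | Reading of Table 5.1.1-1 |
|---|---|---|
| Two doses | evaluable, DLT-free | 0/3 = E |
| Withdrawal | not evaluable, replaced | 0/2, replacement pending |

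**2. What do the plan's own operating characteristics assume?** I enumerated every path of the stated rules (cohorts of 3, at most 6 per dose, Table 5.1.1-1 decisions, Binomial(3, p) outcomes), treating every participant's DLT status as fully known. Percentages selecting below 2 mg/kg / 2 mg/kg / 4 mg/kg, then the DLT rate (%):

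| Scenario | Appendix 5, Table 3 | Enumeration |
|---|---|---|
| 1 | 3.49 / 10.74 / 85.77; 12.4 | 3.49 / 10.70 / 85.82; 12.4 |
| 2 | 3.55 / 15.29 / 81.16; 14.9 | 3.49 / 15.45 / 81.05; 14.95 |
| 3 | 8.19 / 25.13 / 66.69; 19.6 | 8.10 / 25.18 / 66.72; 19.6 |
| 4 | 14.65 / 27.50 / 57.85; 22.1 | 14.48 / 27.68 / 57.84; 22.1 |
| 5 | 22.46 / 37.17 / 40.36; 28.0 | 22.46 / 37.29 / 40.25; 28.0 |

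All agree within 0.2 points. The published performance therefore matches a design in which every counted participant has a complete outcome.

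**3. Effect on the first reading.** Let p be the true 28-day DLT rate.

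- All three fully observed: P(0/3) = (1−p)³. At p = 0.25 this is 0.422; at 0.33 it is 0.301.
- One of three observed only to dose 2, constant hazard: P(0/3) = (1−p)² × (1−p)^f. At p = 0.25: 0.5625 × 0.866 = 0.487 (f = 14/28) and 0.5625 × 0.884 = 0.497 (f = 12/28).
- The same, uniform onset: P(0/3) = (1−p)² × (1−pf). At p = 0.25: 0.5625 × 0.875 = 0.492 and 0.5625 × 0.893 = 0.502.

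At 25%, P(0/3) rises from 42.2% to 48.7–50.2%. At 33%, the same formulas give 30.1% rising to 36.7–38.5%.

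**4. Risk left unseen in a DLT-free leaver.** Under constant hazard this is 1 − (1−p)^(1−f): 13–15% at p = 0.25 and 18–21% at p = 0.33.

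**5. How much survives the S route?** A reading of 1/3 = S adds three subjects, and 1/6 is again E. So P(E by six subjects) = P(0/3) + P(1/3) × (1−p)³, with the second three fully observed.

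- Full observation, p = 0.25: 0.4219 + 0.4219 × 0.4219 = 0.600.
- One leaver with observed DLT probability q: P(1/3) = 2p(1−p)(1−q) + (1−p)²q. With q = 0.134 (constant hazard, f = 14/28): 0.4871 + 0.4001 × 0.4219 = 0.656. With q = 0.107 (uniform onset, f = 12/28): 0.5022 + 0.3951 × 0.4219 = 0.669.

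The gain shrinks to about 6–7 points but does not vanish.

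**The case against.** The best answer is that the two sentences read naturally together. The two-dose sentence sets a general minimum exposure; the withdrawal sentence is a specific exclusion that qualifies it; the synopsis is only a summary. On that reading the Day-18 leaver is already excluded and replaced. This is plausible and probably what was meant, but it is nowhere written, and a reader of the synopsis alone would count the person.

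A reader might infer that the two-dose rule lets the cohort escalate as soon as such a participant leaves. The documents do not support that. Section 5.1.1 times the decision to when the first three subjects have completed the DLT period. Escalation also needs committee agreement after review of safety data from all treated participants, and Section 5.1.1.1 brings in adverse events from those excluded from DLT evaluation. These are real safeguards. They do not say which denominator goes into the table, and review cannot supply data that were never collected. The committee's stated discretion over evaluability covers drug-related dose delays beyond 28 days, not this case.

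Nor does the problem reach everyone who stops early. Participants who only discontinue treatment stay in the study and are followed (Sections 8.1 and 8.2). The conflict needs withdrawal from the study itself, in roughly the two weeks after dose 2, and the documents give no frequency for that.

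It is also fair that S is often only a delay: three further DLT-free subjects occur with probability 0.8³ = 51% to 0.7³ = 34% at true rates of 20–30%.

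**Conclusion.** The contradiction stands and depends on no calculation: one type of participant is classified two ways, without precedence, in the rule that sets the escalation denominator. If the two-dose rule is applied, the count tilts toward E. With one of three leaving just after dose 2 at a true rate of 25%, P(0/3) rises by about 6.5 to 8 points, from 42% to about 49–50%. That size is conditional on such a withdrawal and rests on onset and leaving times that the documents do not give.

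Two stronger readings should be resisted. A reader might infer that no DLT-free participant should count without both two doses and observation to Day 28. That would delete the explicit provision keeping participants who stop for drug-related AEs before a second dose evaluable. A reader might also see a second contradiction in "Unevaluable subjects may be replaced at the same dose level" against the firm replacement of withdrawers. The first covers unevaluable subjects in general and the second a subgroup; requiring replacement of everyone would be a preference, not a correction.

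**What to change.** Reconcile the synopsis and Section 5.1.1.1 by stating in both that the withdrawal exclusion takes precedence over the two-dose criterion: a DLT-free participant who withdraws from the study before the end of the 28-day window for a non-DLT reason is not evaluable and is replaced, even after two doses.

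Keep the provision that participants who discontinue treatment for drug-related AEs before two doses are evaluable, and say that it governs if such a participant also leaves the study. Keep the committee's discretion over long delays, and the permissive replacement wording for other unevaluable subjects.

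The cost is a wording change in two places and, rarely, one more participant. A replacement could need up to 28 days of screening, 3 days to first dose and the 28-day window: 28 + 3 + 28 = 59 days, or about 8 weeks, before that cohort's decision.
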